2.4. Analysis Sets

The analysis sets are defined in Table 2.

Table 2 Populations for Analysis

The following analysis populations apply to Part A, Part B, and Part C, unless otherwise specified:

Population	Description

Randomization Set	All participants who are randomly assigned to the treatment, regardless of the participants' treatment status in the study.	
	Participants will be analyzed according to the treatment group to which they were randomized.	
Full Analysis Set	All participants in Randomization Set who received any study vaccination.	
	Participants will be analyzed according to the treatment group to which they were randomized.	
Immunogenicity Set	All participants in the FAS who have baseline and Day 29 antibody assessment via HAI assay.	
	Participants will be analyzed according to the treatment group to which they were randomized.	
PP Immunogenicity Set	The PP Immunogenicity Set includes all participants in the Immunogenicity Set who received the planned dose of study intervention, complied with the immunogenicity testing schedule for baseline and Day 29 *, and had no significant protocol deviations that impact key or critical data. Participants with RT-PCR-confirmed influenza between Days 1 to 29 will be removed from the PP Immunogenicity Set (Part A only). The PP Immunogenicity Set will be used for all analyses of	
	immunogenicity unless otherwise specified. Participants will be analyzed according to the treatment group to which they were randomized.	
Solicited Safety Set	All participants in the FAS who contributed any solicited AR data.	
	The Solicited Safety Set will be used for the analyses of solicited ARs, and participants will be included in the treatment group corresponding to the study intervention that they actually received.	
Safety Set	All participants in the FAS.	
	The Safety Set will be used for all analyses of safety except for the solicited ARs. Participants will be included in the treatment group corresponding to the study intervention that they actually received.	

Abbreviations: AR=adverse reaction; FAS=Full Analysis Set; HAI=hemagglutinin inhibition; PP=per protocol; RT-PCR=reverse transcription polymerase chain reaction.

* Complied with the immunogenicity testing schedule for baseline and Day 29 is defined as having immunogenicity samples collected before the IP administration and between Day 22 and Day 43 (i.e., -7/+14 days of Day 29).

ModernaTX, Inc. mRNA-1010-P303

For PP Immunogenicity Set, the following major dosing error ranges for planned mRNA-1010 and Fluarix Quadrivalent will be used to determine participant exclusion from the analysis populations:

Actual Vaccine Received	Major Dosing Errors
mRNA-1010 ≤37.5 μg	Yes
mRNA-1010 >37.5 μg – 62.5 μg	No
mRNA-1010 >62.5 μg	Yes
Any Fluarix Quadrivalent or	Ves
Fluzone HD Quadrivalent	105

Table 4 Major Dosing Errors for Participants Randomized into Fluarix Quadrivalent (Part A/B)

Actual Vaccine Received	Major Dosing Errors
Fluarix Quadrivalent ≤45 µg	Yes
Fluarix Quadrivalent >45 µg – 75	No
μg	
Fluarix Quadrivalent >75 µg	Yes
Any Fluzone HD Quadrivalent or	Ves
mRNA-1010	100

For Solicited Safety Set and Safety Set, the following dosing ranges will be used to determine participant's actual treatment group:

- mRNA-1010 50 μg group: If the received dose of mRNA-1010 is >0 μg, and Fluzone and Fluarix Quadrivalent are 0 ug.
- Fluarix Quadrivalent 60 μg group: If the received dose of Fluarix Quadrivalent is >0 μg, and Fluzone and mRNA-1010 are 0 μg.

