 - Participants with immune-mediated diseases which are stable (eg, Hashimoto's thyroiditis and type 1 diabetes) or conditions such as asthma, psoriasis, vitiligo, gout, alopecia areata, or auto-immune ovarian failure, which do not require systemic immunosuppressants per Part A Exclusion Criterion # 13.
- 5. Dermatologic conditions that could affect local solicited AR assessments (eg, tattoos; psoriasis patches affecting skin over the deltoid areas).
- 6. Participant has tested positive for influenza by local health authority-approved testing methods within 150 days prior to Day 1.
- 7. Reported history of anaphylaxis or severe hypersensitivity reaction after receipt of mRNA vaccines or any components of the mRNA-1010 or influenza vaccines, including egg protein.

- 8. Reported history of coagulopathy or bleeding disorder that is considered a contraindication to IM injection or phlebotomy.
- 9. Diagnosis of malignancy within the previous 2 years (excluding nonmelanoma skin cancer).
- 10. History of myocarditis, pericarditis, or myopericarditis within onset of 180 days prior to Day 1 or have not returned to Baseline clinical status. Participants who have not returned to Baseline after their convalescent period will also be excluded.
- 11. History of Guillain-Barre syndrome.
- 12. Any medical, psychiatric, or occupational condition, including reported history of drug or alcohol abuse, that, in the opinion of the Investigator, might pose additional risk due to participation in the study or could interfere with the interpretation of study results.

Prior/Concomitant Therapy

- 13. Participant has received systemic immunosuppressants for >14 days in total within 180 days prior to Day 1 (for corticosteroids, ≥10 mg/day of prednisone or equivalent) or is anticipating the need for systemic immunosuppressive treatment at any time during participation in the study. Inhaled, nasal, and topical steroids are allowed. Intra-articular and epidural steroid injections are not allowed within 28 days before and/or after study intervention dosing.
- 14. Participant has received any vaccine authorized or approved by local health agency ≤28 days prior to study intervention dosing (Day 1) or plans to receive a vaccine authorized or approved by local health agency within 28 days before or after study intervention dosing.
- 15. Participant has received a licensed seasonal influenza vaccine within 5 months (150 days) prior to Day 1.

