2.6.6.2. Recording of Concomitant Medications, Concomitant Vaccinations and Concomitant Procedures

The following concomitant medication(s) and vaccine(s) must be recorded in the eCRF:

- Any vaccine (authorized or investigational) administered in the prior 12 months. For authorized influenza vaccines, detailed information regarding which vaccine was administered should be provided if available.
- All prohibited therapies (Section 2.6.6.1) at the time of the Day 1 Visit.
- All concomitant medications taken at the time of the Day 1 Visit through 28 days after study intervention dosing. Antipyretics and analgesics taken prophylactically (ie, taken in the absence of any symptoms in anticipation of an injection reaction) will be recorded as such.
- All non-study vaccines taken through 181 days after study intervention dosing.
- Systemic steroids (≥10 mg/day prednisone or equivalent), immunosuppressants, immunoglobulins and long-acting biological therapies that affect immune responses (eg infliximab), and/or blood products administered at any time during the study period after the study intervention.
- Any concomitant medications relevant to or for the treatment of an SAE, AESI, or MAAE from Day 1 through Day 181 (Month 6)/EoS.
- The participant will be asked in the eDiary if they have taken any antipyretic or analgesic to treat or prevent fever or pain within 7 days after study intervention dosing, including the day of dosing. Reported antipyretic or analgesic medications should be recorded in the source document by the clinic staff during the clinic/in-person visit and safety phone call after study intervention dosing or via other participant interactions (eg, telephone calls).
- All concomitant procedures/surgeries at any time during the study period after study intervention dosing.

Concomitant medications (including vaccinations) will be coded using the WHO Drug Global.

2.6.6.3. Concomitant Medications and Vaccines That May Lead to the Elimination of a Participant From Per-protocol Analyses

The use of the following concomitant medications and/or vaccines will not require withdrawal of the participant from the study but may determine a participant's evaluability in the PP analysis (analysis sets are described in Section 2.9.4):

• Any investigational or nonregistered product (drug or vaccine) other than the study intervention used during the study period.

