- Immunosuppressants administered chronically (ie, more than 14 days in total) during the study period. For corticosteroids, this will mean that prednisone ≥10 mg/day or the equivalent is not permitted. Intra-articular and epidural steroids are not allowed within 28 days before and/or after study intervention dosing. Inhaled, nasal, and topical steroids are allowed.
- Long-acting, immune-modifying drugs administered at any time during the study period (eg, infliximab).
- An authorized or licensed vaccine administered within 28 days of study intervention dosing.
- Immunoglobulins and/or any blood products administered during the study period.

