7.8. Estimands and Estimand Specifications

The following applies to Part A, Part B, and Part C, unless otherwise specified:

Table 16 Intercurrent Events

Label	Intercurrent Event Type
IcEv1 (early discontinuation or unrelated death)	Early discontinuation from study or unrelated death prior to Day 29, the first post-treatment immunogenicity result available.
IcEv2 (alternative influenza vaccine)	Use of alternative Influenza vaccine prior to Day 29.
IcEv3 (COVID-19 vaccine)	Use of COVID-19 vaccine prior to Day 29.
IcEv4 (prohibited medications)	Use of prohibited medications deemed to impact on immunogenicity prior to Day 29.
IcEv5 (early infection)	Infection starting up to 29 days after IP injection.
IcEv6 (wrong vaccination)	Receiving wrong vaccination.

Abbreviation: IcEv: intercurrent event.

Table 17 Summary of Primary Immunogenicity Estimands with Rationale for Strategies to

Address Intercurrent Events (Part A)

Objective: To evaluate the humoral immunogenicity of mRNA-1010 relative to that of a licensed active comparator (Fluarix Quadrivalent) against 4 vaccine-matched influenza virus A and B strains at Day 29 based on GMT			
Estimand Label	Primary Immune Estimand 1a (on the PP Immunogenicity Set)	Supplementary Immune Estimand 1b	
Estimand Description	Immune response to influenza measured as GMT of vaccine- matched anti-HA level as measured by HAI assay on Day 29 in adults aged at least 18 years inclusive who receive IP administration and complied with immunogenicity blood sampling to have a baseline and Day 29 antibody assessment without significant protocol deviations impacting immune response and no RT-PCR- confirmed influenza between Days 1 to 29.	Immune response to seasonal influenza measured as GMT of vaccine-matched anti-HA level as measured by HAI assay on Day 29 in adults aged at least 18 years or inclusive who receive IP administration irrespective of any significant protocol deviations impacting immune response and complied with immunogenicity blood sampling to have a baseline and Day 29 antibody assessment as measured by HAI assay.	

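### The primary set accepts Day 29 blood up to Day 43, but the vaccine exclusions end at about Day 28 or 29 and are not tied to the draw date

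*SAP*

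**What the plan says.** **Blood window.** A footnote to SAP Table 2 (Section 2.4) treats the sampling schedule as met when the post-dose sample falls "between Day 22 and Day 43 (i.e., -7/+14 days of Day 29"). The table applies to Parts A, B and C. The schedules of activities in the protocol (Tables 1, 7 and 11) and in SAP 7.1 allow -7 to +3 days. Protocol 2.8 makes a visit outside that window a protocol deviation but asks that it still be completed if possible.

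**Vaccine exclusions.**
- SAP Table 16, IcEv2: "Use of alternative Influenza vaccine prior to Day 29". IcEv3 has the same limit for COVID-19 vaccine.
- Protocol 2.6.6.3, events that may affect per-protocol evaluability: "An authorized or licensed vaccine administered within 28 days of study intervention dosing".
- Exclusion Criterion 14, worded alike in all Parts, bars anyone who "plans to receive a vaccine authorized or approved by local health agency within 28 days before or after study intervention dosing".

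**Infection.** SAP Table 2: "Participants with RT-PCR-confirmed influenza between Days 1 to 29 will be removed from the PP Immunogenicity Set (Part A only"). IcEv5 reads "Infection starting up to 29 days after IP injection" and is handled by principal stratum in the primary estimands of all three Parts (SAP Tables 17 to 19).

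**Not cut off at Day 28 or 29.** Protocol 2.6.6.3 also lists "Any investigational or nonregistered product (drug or vaccine) other than the study intervention used during the study period", and it covers chronic immunosuppressants, long-acting immune-modifying drugs, immunoglobulins and blood products over the study period.

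**Data held.** Protocol 2.6.6.2 requires recording of "All non-study vaccines taken through 181 days after study intervention dosing".

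**The concern.** The rationale in SAP Tables 17 to 19 describes the primary estimand as a sub-population in which none of the listed intercurrent events occurred. For a titre endpoint, the relevant period runs from dosing to the draw. Here the draw may come up to two weeks after the exclusions have stopped.

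Take a participant who receives a licensed influenza vaccine on Day 31 and is bled on Day 40. The vaccination is outside the 28-day restriction, licensed vaccines are not on the prohibited-therapy list (Protocol 2.6.6.1), and the SAP counts the sample as on schedule. The late visit is a deviation under the protocol, but the SAP footnote expressly accepts it. The titre then enters the GMR and the seroconversion rate as a response to the assigned vaccine.

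The mismatch also runs the other way. A participant bled on Day 22 and vaccinated on Day 26 meets IcEv2 and may be removed, although the vaccination came after the sample.

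The planned outputs would show little of this. The SAP 2.5.2.4 summary of non-study influenza vaccine ends at 28 days, leaving only a listing. The supplementary analysis on the Immunogenicity Set handles these events by treatment policy, so it does not remove them either.

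**Working it through.** **1. The windows.** SAP footnote: 29 - 7 = Day 22 and 29 + 14 = Day 43, as stated. Schedules of activities: 29 - 7 = Day 22 and 29 + 3 = Day 32. SAP 2.5.1 makes the injection date Day 1, so 28 days after dosing is Day 29 and 29 days after injection is Day 30.

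**2. The uncovered days.** An exposure must precede the draw to affect it, so the last relevant day is the day before the draw.

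| Rule | First uncovered day | Draw on Day 32 | Draw on Day 43 |
|---|---|---|---|
| IcEv2, IcEv3 (before Day 29) | 29 | Days 29-31: 3 days | Days 29-42: 14 days |
| Protocol 28-day vaccine rule | 30 | Days 30-31: 2 days | Days 30-42: 13 days |
| RT-PCR removal, Part A (Days 1 to 29) | 30 | Days 30-31: 2 days | Days 30-42: 13 days |

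With exclusion run to each participant's own draw date, every entry is zero.

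**3. What it could do to the tests.** Let f be the share of per-protocol participants with an exposure before a late draw. The documents do not give f; 1% and 5% are assumptions. Inputs from the Part B and C sample-size sections are 1275 per arm, margins of 10 points and 1.5, and a log-scale SD of 1.5. The comparator SCR is 49% (Part B, B strains). Errors are one-sided and per endpoint, by normal approximation, with the true effect placed on the margin (2.5% when f = 0).

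*GMT, proportional boost.* A k-fold boost in a share f multiplies that arm's GMT by k^f. For k = 4 (assumed) and f = 1%, 4^0.01 = 1.014. In one arm only, the GMR moves by 1.4%, up or down according to the arm. With the same k and f in both arms it cancels and the GMR is unchanged.

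*GMT, levelling.* If exposed participants end at the same mean titre in both arms, ln GMR shrinks by the factor (1 - f). The standard error is 1.5 × √(2/1275) = 0.0594. Error = Φ(f × ln 1.5 / 0.0594 - 1.96), which is 2.9% at f = 1% and 5.3% at f = 5%.

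*SCR.* If every exposed participant becomes a seroconverter, p becomes p + f(1 - p). With true rates of 49% and 39% the standard error is about 0.0196.

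| Exposure | f | Difference (points) | Error |
|---|---|---|---|
| Both arms equally | 1% | -9.9 | 2.8% |
| Both arms equally | 5% | -9.5 | 4.4% |
| mRNA-1010 arm only | 1% | -10 + 0.61 = -9.39 | 5.0% |
| Comparator arm only | 1% | -10 - 0.51 = -10.51 | 1.3% |

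The last row: (0.10 - 0.1051)/0.0196 - 1.96 = -2.22, and Φ(-2.22) = 1.3%.

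Success needs all eight endpoints, so error for a whole Part cannot exceed that for any single endpoint on its margin.

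**The case against.** **Day 29 may mean the visit.** IcEv1 in Table 16 ties Day 29 to the first available post-treatment result, and SAP 7.3 maps scheduled samples to the nominal visit. IcEv2 to IcEv4 could therefore be read as before the Day 29 result. That reading is plausible. It does not reach the 28-day rule in Protocol 2.6.6.3 or IcEv5, which count days. If it is what was meant, the repair is a clarification.

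**Draws after Day 32 are off schedule.** This is correct: they are deviations under Protocol 2.8. For in-window draws only 2 to 3 days are exposed, which leaves little time for a titre to rise. The longer gap concerns late samples that the SAP chooses to accept.

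**The deviation rules are still to be finalised (SAP 2.5.2.5).** They could catch some cases, but a licensed vaccine after the 28-day limit breaks no stated rule. Likewise, Protocol 2.6.6.3 says the listed uses may affect evaluability, so removal of the Day 22/Day 26 participant is possible rather than certain.

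**Stronger readings that a reader might infer.** One is that the gap favours noninferiority. The documents do not show this: equal proportional boosts cancel in the GMR, and exposure confined to the comparator arm works against noninferiority. Another is that the SCR would rise by the full exposed share. That needs every exposed participant to be a non-converter otherwise, whereas the planning rates are 48% to 70%. A third is that prohibited medications (IcEv4) have the same gap. The protocol already covers them for the whole study.

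**Conclusion.** The mismatch is in the text. Blood is accepted to Day 43, the vaccine exclusions end at about Day 28 or 29, and no rule refers to the draw date. It bears on the primary analysis and conflicts with the stated aim of a population without intercurrent events. The gap is 2 to 3 days for draws within the visit window and 13 to 14 days for the latest accepted draw.

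The effect is probably small. With 1% of participants exposed equally in both arms, per-endpoint error moves from 2.5% to about 2.8% or 2.9%. It matters more only if exposure reaches several percent or differs by arm, and its direction then depends on the arm. All of this rests on assumed exposure shares and boosts. Whether any titre was actually affected cannot be known from the documents.

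A reader might infer that Part A's primary set should be redefined. The documents do not support that: Protocol 5.7.1 (10 October 2023) already reports Part A as meeting noninferiority, before SAP version 2.0 (3 April 2024). Changing the primary set now would be a change made with the result known.

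A related inconsistency concerns infection. IcEv5 is assigned to principal stratum in all Parts, but Table 2 removes RT-PCR-confirmed influenza in Part A only, and the respiratory infection assessments of Protocol 2.8.3.4 are also limited to Part A. The SAP does not say how IcEv5 operates in Parts B and C.

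**What to change.** **Parts B and C, before database lock and unblinding.** In SAP Table 16, define IcEv2 and IcEv3 as use after dosing and before the date of the blood sample used as the Day 29 titre. Use the same definition for the matching vaccine exclusion from the PP Immunogenicity Set, and state that it replaces the 28-day limit for that purpose.

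**Part A.** Leave the reported primary analysis as it stands. Apply the draw-date rule to non-study vaccines and RT-PCR-confirmed influenza as a labelled sensitivity analysis.

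**Other events.** IcEv4 needs only consistent wording. Reconcile IcEv5 with the Part A-only removal in Table 2 by stating how it is applied, or that it is not, in Parts B and C.

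**Cost.** SAP wording and one date comparison in the programming. Non-study vaccination dates are already recorded through 181 days, so no new data are needed. A few participants may move into or out of the set.

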2.5. Statistical Analysis

2.5.1. General Considerations

SoA is presented in Section 7.1.1.

The following general consideration for analysis applies to Part A, Part B, and Part C, unless otherwise specified:

Continuous variables will be summarized using the following descriptive summary statistics: the number of participants (n), mean, standard deviation, median, min, and max.

Categorical variables will be summarized using counts and percentages. For the summary statistics of all numerical variables unless otherwise specified, the display precision will follow programming standards, see Section 7.2.

When count data are presented, the percentage will be suppressed when the count is zero to draw attention to the non-zero counts. A row denoted "Missing" will be included in count tabulations where specified on the shells to account for dropouts and missing values. The denominator for all percentages will be the number of participants in that vaccination group within the analysis set of interest, unless otherwise specified.

Baseline value is defined as the most recent non-missing measurement (scheduled or unscheduled) collected before the study vaccine injection, unless otherwise specified. For immunogenicity tests and NP swab tests, the baseline is defined as the most recent non-missing result/measurement (scheduled or unscheduled) collected before or on the date (and time, if applicable) of injection (Day 1).

Age: unless otherwise specified, age is calculated as the age at screening. In the analyses for subgroups defined by age, age at screening will be used for derivation of age groups.

Vaccination groups:

The following vaccination groups will be used for summary purposes:

• mRNA-1010 50 µg (for Part A, Part B, and Part C)

ModernaTX, Inc. mRNA-1010-P303

Fluarix Quadrivalent 60 µg (for Part A and Part B), or Fluzone HD Quadrivalent 240 µg (for Part C)

All analyses and data summaries/displays will be provided by vaccination group using appropriate analysis population, unless otherwise specified. Summaries may also contain a display for all vaccination groups pooled together (i.e., overall group).

Study day relative to injection will be calculated as below:

- Study day prior to injection will be calculated as: date of assessment/event date of injection.
- Study day on or after injection will be calculated as: date of assessment/event date of injection +1.

Unscheduled visits: measurements from unscheduled visit will be included in analysis as follows:

- In scheduled visit windows per specified visit windowing rules.
- In the derivation of baseline/last on-treatment values.
- In the derivation of max/min on-treatment values and max/min change from baseline values for safety analyses.
- In individual participant data listings as appropriate.

Visit windowing rules: The analysis visit windows for protocol-defined visits are provided in Section 7.3.

Analysis Periods:

The following analysis periods will be used for safety analyses in the study:

- 7 days post-vaccination: this period includes the day of vaccination and 6 subsequent days. This analysis period will be used for solicited local/systemic ARs and SAEs that occur during this time.
- Up to 28 days post-vaccination: this period starts from the day of vaccination and spans 28 days to include the day of vaccination and 27 subsequent days. This analysis period will be used for unsolicited AE, except for solicited AR, unless specified otherwise.

- Up to data cutoff date: this period starts from day of vaccination and continues through the data cutoff date applied at planned analyses as specified in Section 2.5.7.
- Overall study period/Throughout the study: this period starts on Day 1 and continues through the earliest of the following: study completion, discontinuation from the study, or death.

For the Day 29 primary analysis, the analysis will include all participants' immunogenicity data and safety data collected up to a DCO Date. DCO determination will be based on the Day 29 visit date of the last dosed participant in the Part, the needed time for data entering (which may be a few additional days), and the actual DCO date will be provided by the Clinical Operation of the study.

Incomplete/Missing Data:

- Imputation rules for missing prior/concomitant medications, non-study vaccinations and procedures are provided in Section 7.4.
- Imputation rules for missing AE dates are provided in Section 7.4.
- For summarizations of GMTs, antibody titers reported as below LLOQ will be replaced by 0.5 x LLOQ. Values that are greater than ULOQ will be converted to the ULOQ.
- Other incomplete/missing data will not be imputed, unless otherwise specified.

Subgroups:

Subgroup Variable *	Categories
Age Group 1	≥ 18 to <50 years old
	\geq 50 to <65 years old
	\geq 65 years old
Age Group 2	≥ 18 to <50 years old
	\geq 50 to <65 years old
	\geq 65 to <75 years old
	\geq 75 years old
Flu Vaccine Status in the past 5 to 12	Yes
months (only for immunogenicity	No
analyses)	

Table 5 Definition for Subgroups (Part A)

Race	White
	Black or African American
	Asian
	American Indian or Alaska Native
	Native Hawaiian or Other Pacific Islander
	Other (combining Not Reported and Unknown)
Sex	Male
	Female
BMI (only for immunogenicity	$<30 \text{ kg/m}^2$
analyses)	$\geq 30 \text{ kg/m}^2$

*Subgroup derivations will be based on the information from eCRF.

If the number of participants in a subgroup is less than 10% of sample size in the analysis set, it may be combined with other subgroups for the subgroup analyses.

